	• Inotrope score calculated each hour post-operatively from the time of separation from bypass until the completion of study drug. Additionally, the total inotrope score over time until Day 28 or hospital discharge will be derived.
	 Hemodynamic improvement (heart rate, systemic arterial blood pressure, oxygen saturation, and central venous pressure)
	 Length of time of intubation
	Longin of time of intubation

11 August 2017

11 August 2017	
	 Length of time on vasodilators
	Length of hospitalization
	 Thoracotomy output; duration and volume of chest tube drainage
	 Plasma concentrations of L-citrulline
Safety	 Adverse events
Assessments	 Incidence of refractory hypotension
	Laboratory values
Statistical Methods:	Continuous variables will be summarized with means, standard deviations, medians, lower and upper quartiles, minimums and maximums. Frequencies and percentages will be used to summarize categorical variables.
	For time-to-event analyses censoring information will be used. No other imputation of missing values (e.g., no last observation carried forward (LOCF)) will be used, unless stated otherwise.
	Analysis sets:
	Safety Analysis Set (SAF):
	All randomized subjects who received surgery and study medication (independent of whether it is L-citrulline or placebo) will be valid for the SAF. The SAF will be used for the evaluation of the safety assessments.
	Full Analysis Set (FAS):
	The FAS includes all subjects who received surgery. The FAS serves as the primary efficacy analysis set.
	Modified Full Analysis Set (mFAS):
	The mFAS includes all subjects who received surgery and study medication (independent of whether it is L-citrulline or placebo). The mFAS serves as a sensitivity population for the efficacy analyses.
	Per-protocol Analysis Set (PP):
	The PP includes all subjects included in the SAF who had no significant protocol deviations and completed through Day 28 or until discharge from the hospital (end of study follow-up). The PP will only be analyzed for main efficacy outcome measures.
İ	

Asklepion GROWTH HEALTH PINNOVATION

11 August 2017

ANALYSIS OF PRIMARY EFFICACY ENDPOINT:

Hypothesis to be tested:

H0: Composite endpoint within the L-citrulline group is equal to that of the placebo group

H1: Composite endpoint within the L-citrulline group is unequal to that of the placebo group

H0 will be tested using a Wilcoxon-rank-sum test. The level of significance is 1% (two-sided).

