3.2 Secondary Endpoints

3.2.1 Secondary Efficacy Endpoints

- Length of time on mechanical ventilation
- Length of time on positive pressure ventilation
- Length of time of inotrope use
- Inotrope score calculated each hour post-operatively from the time of separation from bypass until the completion of study drug; additionally, the total inotrope score over time until Day 28 or hospital discharge will be derived
- Hemodynamic improvement (heart rate, systemic arterial blood pressure, oxygen saturation, and central venous pressure)
- Thoracotomy output; duration and volume of chest tube drainage
- Length of time of intubation
- Length of PICU stay
- Length of time on vasodilators
- Length of hospitalization
- Plasma concentrations of citrulline

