6.2 Efficacy and Safety Measurements Assessed

6.2.1 Efficacy Assessments

6.2.1.1 Mechanical Ventilation

The definition of mechanical ventilation includes invasive mechanical ventilation or non-invasive mechanical ventilation including BPAP or CPAP. Length of time on mechanical

ventilation will be assessed from the time of separation from CPB until mechanical ventilation is discontinued.

6.2.1.2 *Inotropes*

Inotropes are defined as dopamine, dobutamine, milrinone, epinephrine, phenylephrine, and norepinephrine. Inotrope use will be assessed from the start of CPB until the subject is discharged from the hospital or at Day 28.

Total Inotrope Score = Dopamine + Dobutamine + 10*Milrinone + 100*Epinephrine + 100*Phenylephrine + 100*Norepinephrine.

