Additionally, the total inotrope score over time until Day 28 or hospital discharge will be derived and analyzed using a Wilcoxon-Rank sum test and an ANOVA with a fixed effect for treatment group.

The total inotrope score will be imputed to zero after the bypass pump has been removed. It will also be imputed as zero for patients not using inotropes at all. For any missing scores between two non-missing scores they will be imputed using the most recent non-missing score (the last observation carried forward principle).

Hemodynamic Improvement

Hemodynamic evaluations include heart rate, systemic arterial blood pressure, oxygen

saturation, and central venous pressure. The absolute changes from baseline at hours 1, 2, 4, 12, 24, and 48 will be compared between groups using an ANOVA with a fixed effect for treatment group and baseline level.

An ANOVA adding site and site-by-treatment group interaction will be conducted as a sensitivity analysis. If the p-value for the site-by-treatment group interaction is lower than 0.1 the analysis will also be provided by site. Summary tables describing descriptive measurements will be generated for absolute values and absolute change from baseline values for all observed time points.

Length of time on intubation

The length will be derived as the time in hours from separation from CPB until discontinuation of intubation. Any duration of re-use of intubation will continue to accrue. If a subject did not use any intubation the length is set to 0. As a sensitivity analysis, subjects with no use of intubations will be excluded. For subjects who died before discharge from the hospital or before Day 28, respectively, the observed length of time on intubation will be used. As sensitivity analyses subjects who died will (1) be excluded from analysis and (2) be assigned a length of time on intubation of 28 days.

For the length of time on intubation the same analyses as described for the primary endpoint will be applied.

Length of PICU stay

The length of PICU stay will be calculated as the total number of days postoperative until discharge from PICU. For subjects who died before discharge from PICU or before Day 28, respectively, the observed length of PICU stay will be used. As sensitivity analyses subjects who died will (1) be excluded from analysis and (2) be assigned a length of PICU stay of 28 days.

For the length of PICU stay the same analyses as described for the primary endpoint will be applied.

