2.2 Secondary Efficacy Variables

The following secondary efficacy parameters will be analyzed:

- Length of time on mechanical ventilation
- Length of time on positive pressure ventilation
- Length of time of inotrope use
- Inotrope score
- Hemodynamic improvement
- Length of time of intubation
- Length of pediatric intensive care unit (PICU) stay
- Length of time on vasodilators
- Length of hospitalization
- Thoracotomy output - duration and volume of chest tube drainage
- L-citrulline plasma levels

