4.4.2 Analysis of Secondary Efficacy Variables

No formal statistical hypotheses are specified for the secondary endpoint variables. Nonetheless statistical testing methods will be applied to compare treatment groups. A significance level of 5% (two-sided) will be used for such analyses. Secondary efficacy endpoints will be analyzed using FAS, mFAS and PP. All secondary analyses are considered exploratory.

Length of time on mechanical ventilation

The same definitions and analyses as described for the primary endpoint will be applied. As sensitivity analysis, length of time on mechanical ventilation will be calculated starting on “start date/time” of mechanical ventilation.

Length of time on positive pressure (non-invasive) ventilation

Positive pressure ventilation describes non-invasive mechanical ventilation. The same definitions (only using non-invasive ventilation stop date/time and non-invasive ventilation breaks: BPAP, CPAP, HFNC, and other non-invasive) and analyses as described for the primary endpoint will be applied.

Length of time of inotrope use

The same definitions and analyses as described for the primary endpoint will be applied. As sensitivity analysis, length of time of inotrope use will be calculated starting on first “start date/time” of inotrope use.

Inotrope score

The total inotrope score at each hour post-operatively from the time of separation from bypass until the completion of study drug will be calculated as:

Total Inotrope Score = Dopamine + Dobutamine + 10*Milrinone + 100*Epinephrine +100*Phenylephrine + 100*Norepinephrine.

The score will be calculated for each hour post separation from CPB (see section 4.4.1) until 48 hours post separation. If within the time interval of hours x after the separation from CPB any inotrope was given, the total score will be calculated and used for analysis.

Example for a patient's inotrope documentation:

- 12:00: Separation from CPB
- Dopamine: 100 mcg/kg/min from 12:00 to 13:00,
- Dobutamine 100 mcg/kg/min from 13:00 to 13:30, 14:01 to 14:59, and 16:00 to 17:00.

The times of interest at 1, 2, 3, ... hrs will be derived as time of separation from CPB + 59, 119, 179, ... minutes. I.e., the times of interest and the total inotrope score would then be calculated as follows:

- 1 hrs (12:00-12:59) = 100 (Dopamine (100) documented 12:00-13:00)
- 2 hrs (13:00-13:59) = 200 (Dopamine (100) documented 12:00-13:00
Dobutamine (100) documented 13:00-13:30)

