Actually the exact start and end date/times of inotropes will be documented in the CRF, therefore the length of time of inotrope use will be derived in minutes.

Additionally, to be consistent to the time of mechanical ventilation, the time of separation from CPB will be used as starting point instead of time of first use.

Also, it is stated "For any missing scores between two non-missing scores they will be imputed using the most recent non-missing score (the last observation carried forward principle)." Due to the inotrope documentation as described above the LOCF principle is not to be applied.

6 Literature

n/a

7 Appendices

- Appendix A: List of generated summary tables, listings, and graphs

8 Signatures**Statistician:**

[name]
FGK Clinical Research GmbH
[name]
[name]
Germany

04 Oct 2018

Date (ddmmmyyyy)

[name]

Signature

Sponsor:

[name]
Aklepion Pharmaceuticals, LLC
Chief Medical Officer
[name]
[name]

02 Oct 2018

Date (ddmmmyyyy)

[name]

Signature

[name], BA
Aklepion Pharmaceuticals, LLC
Director of Clinical Operations
[name]
[name]

02 October, 2018

Date (ddmmmyyyy)

[name]

Signature

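### The SAP text leaves out one of the protocol's two inotrope-score components, the total score to Day 28 or discharge, and does not declare the change

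*SAP*

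**What the plan says.** **Protocol.** After the hourly score, section 3.2.1 adds a second component to the endpoint: "additionally, the total inotrope score over time until Day 28 or hospital discharge will be derived". The synopsis says the same: "Additionally, the total inotrope score over time until Day 28 or hospital discharge will be derived". Section 7.1.4 gives this component its own between-arm comparison: "Additionally, the total inotrope score over time until Day 28 or hospital discharge will be derived and analyzed using a Wilcoxon-Rank sum test". An ANOVA with a fixed treatment effect accompanies that test. The collection window is long enough to support it (section 6.2.1.2): "Inotrope use will be assessed from the start of CPB until the subject is discharged from the hospital or at Day 28".

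**SAP.** Section 2.2 lists only "Inotrope score", with no time horizon. Section 4.4.2 then sets the window: "The score will be calculated for each hour post separation from CPB (see section 4.4.1) until 48 hours post separation". The hourly values are tested hour by hour with a Wilcoxon test and an ANOVA, and together with a repeated-measures ANOVA. Section 4.8 gives zero-score rules and nothing for a longer score. Section 5 lists three inotrope changes: minutes instead of hours, separation from bypass as the starting point, and no carrying forward of missing scores ("Due to the inotrope documentation as described above the LOCF principle is not to be applied").

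**The concern.** The SAP presents itself as the detailed version of the methods in global protocol 4.3.1 and has a section reserved for departures. The carry-forward rule that section 5 withdraws sits in the same part of protocol 7.1.4 as the longer score. A reader of section 5 would therefore conclude that nothing else about the score had changed.

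Two things are at stake. First, a between-arm comparison promised in the synopsis, the endpoint list and the statistics section would not be produced. Dropping it without a stated reason leaves the sponsor open to a selective-reporting question. Second, the score carries information that duration does not. It weights drugs by 1, 10 or 100 and multiplies by rate, so two children with the same length of use can differ greatly in score. After 48 hours, the SAP as written has no measure that captures this.

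**Working it through.** There is no sample size, power or alpha figure to reproduce here. The check is a comparison of the two documents.

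1. **Hourly component.** Protocol 7.1.4: hourly scores from separation from bypass to the end of study drug, with Wilcoxon, ANOVA and repeated-measures ANOVA. SAP 4.4.2: the same three analyses on hourly scores. *Carried over.*

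2. **Day 28 or discharge component.** Protocol 7.1.4: "the total inotrope score over time until Day 28 or hospital discharge will be derived and analyzed using a Wilcoxon-Rank sum test", plus an ANOVA. SAP 2.2, 4.4.2 and 4.8: no derivation, summary or test. *Not carried over.*

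3. **Could the SAP's repeated-measures ANOVA be the missing item?** No. Protocol 7.1.4 lists it separately, before the longer score. In the SAP it has only the hourly values as input, and these stop at 48 hours.

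4. **Could the SAP window be read as reaching Day 28?** No. SAP 4.4.2 gives two end points for the hourly score, completion of study drug and 48 hours after separation. Neither approaches Day 28 for a child with prolonged support.

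5. **Is the change declared?** No. None of the three inotrope changes in SAP section 5 concerns the longer score.

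6. **Window length.** The maximum follow-up is 28 × 24 = 672 hours, and 48 / 672 = 7.1%. This compares window lengths only. It does not say how much inotrope exposure lies outside the SAP window, because many children may have stopped inotropes or gone home well before Day 28.

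7. **What still covers later use.** SAP 4.4.1 measures length of inotrope use to discharge or Day 28. It enters the primary composite and is also analysed as a secondary endpoint. Late use therefore counts as time, but not as dose.

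8. **Are the data available?** Protocol 6.2.1.2 assesses inotropes to discharge or Day 28. SAP section 5 says exact start and end times are on the CRF, and the worked example in SAP 4.4.2 uses documented rates with start and stop times. The inputs for a time-weighted total appear to exist, although the CRF itself was not available.

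**The case against.** The strongest reply is that this is a reconciliation item on one part of an exploratory endpoint. SAP 4.4.2 classes every secondary analysis as exploratory. The hourly component is intact, and inotrope score is not among the secondary objectives in protocol section 2.2 or SAP section 1.2. The protocol also never says how the score is to be aggregated over time, so any derivation is a new definition and not a pure restoration. The SAP further rests on an EU protocol (version 2.0) later than global 4.3.1, and its tables are listed in Appendix A; neither was available. All of this stands and limits the weight of the point. It does not remove it: global 4.3.1 still requires the comparison, and a table listed in an appendix could not replace a derivation and test absent from the SAP body.

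Three stronger readings are tempting, and the documents do not support them:

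- *A whole secondary endpoint is lost, or late inotrope use is ignored.* Only one component is missing, and duration to Day 28 or discharge is still tested.
- *The pilot shows that much of the treatment difference falls after 48 hours.* Protocol section 1.4 says pilot inotrope use was documented only to hour 48, with ventilation time used beyond that. Composite values above 48 hours in Table 2 are therefore ventilation time and say nothing about later inotrope use.
- *The omission creates a multiplicity problem through the many hourly tests.* Those tests are the protocol's own plan and would remain if the longer score were restored.

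**Conclusion.** The discrepancy is real and should be resolved before unblinding. One of the two components of the inotrope-score endpoint, with its own Wilcoxon test and ANOVA in the protocol, is missing from the SAP text, and its removal is not declared. The consequence is the loss of the only dose-weighted inotrope measure after 48 hours. The primary test, alpha and sample size are unaffected. How much clinical information is lost cannot be quantified from these documents. The conclusion rests on global protocol 4.3.1 being the governing text and assumes that neither the EU protocol nor SAP Appendix A removes or supplies the analysis. Nothing in the documents shows whether the omission was deliberate.

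**What to change.** Before unblinding, do one of the following.

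- **Restore the score in SAP 4.4.2.** State a per-child derivation. One option is the weighted score summed over time from separation from bypass to the earlier of discharge or Day 28, set to 0 for a child with no inotrope use. Handle deaths and early withdrawals as for the length-of-time endpoints, including the death sensitivity analyses. The rule that assigns 28 days to a child who died has no direct equivalent for a score, so the SAP must say what replaces it. Compare arms with the protocol's Wilcoxon test and ANOVA in the FAS, mFAS and PP. Keep the hourly analyses, which the protocol also requires.
- **Or declare the removal in SAP section 5**, with the reason.

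Also check Appendix A and the EU protocol, so that all the documents agree. Restoring the score costs one derived variable, a paragraph of SAP text and the matching tables. No new data collection should be needed if rates are recorded on the CRF as the SAP's worked example implies. Declaring the removal costs a sentence or two.

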- ⁷ Hemodynamic monitoring includes heart rate, systemic BP, O₂ saturation, CVP, and PAP measurements (if data is available). **Baseline values are first recorded in the operating room (OR)** by Anesthesia. Results will be *monitored* during surgery according to the Institution's standard of care, but results will only be *recorded* approximately every 15 minutes. Standard of care will continue to be followed from time of post-op admission to the PICU through 48 hours. Results at 1, 2, 4, 12, 24, and 48 hours *from baseline (in OR)* must be obtained and recorded.
- ⁸ Arterial Blood Gas (ABG) includes PaO₂, PaCO₂, HCO₃, and pH. ABGs will be drawn according to the Institution's standard of care. Baseline results are first recorded in the OR by Anesthesia. All results obtained during surgery, and from the time of post-op admission to the PICU until removal of the arterial line or through 48 hours (whichever occurs first), will be recorded.
- ⁹ Begin bolus of intravenous (i.v.) L-citrulline at 150 mg/kg or placebo at initiation of CPB & add L-citrulline at a concentration of 200 μmol/L or placebo given as a bolus during bypass. The 200 μmol/L dose may be administered as a one-time bolus or multiple administrations, to maintain the concentration at 200 μmol/L.
- ¹⁰ Collect 1.0 mL of blood for plasma L-citrulline levels (*30 minutes after decannulation from CPB in OR; prior to bolus*). All L-citrulline plasma samples must be processed within four hours of being drawn, stored at -20°F (-28.8°C) or below, and sent on dry ice to the central lab.
- ¹¹ Bolus of 20 mg/kg of L-citrulline or placebo 30 minutes after decannulation from CPB immediately followed by a continuous infusion of L-citrulline at 9 mg/kg/hr or placebo
- ¹² Collect 1.0 mL of blood for plasma L-citrulline levels (5 minutes after bolus). All L-citrulline plasma samples must be

⁵Blood collected for intra-op laboratory values and plasma L-citrulline levels (**10 minutes after study drug administered**); (1.0 mL for plasma L-citrulline). All L-citrulline plasma samples must be processed within four hours of being drawn, stored at -20°F (-28.8°C) or below, and sent on dry ice to the central lab.

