Placebo will be matched for volume using suitable fluid recognized as standard of care for such procedure (e.g. normal saline or Plasmalyte without L-citrulline added).

All study medications will be prepared and provided by each site's investigational pharmacy. A pharmacy manual will be provided to the hospital or institution Investigational Pharmacist. The manual will contain detailed instructions for the preparation of the investigational product. The manual will include specific directions on randomization procedures, preparation of study drug or placebo and labeling of product for administration. The label should contain subject information (e.g. subject initials, subject identification number), study number, volume of product to be administered, and the date of administration. However, the label may not contain any information that identifies the actual product being administered.

All study medications will be administered by the Investigator or by medically trained personnel under his/her supervision (e.g., the anesthesiologist, perfusionist, PICU personnel, etc.).

Doses will be given by a central i.v. catheter that will be emplaced after induction of anesthesia or via the bypass circuit. Separate i.v. access is not required for the study drug. The study drug is isotonic and can run through either a peripheral i.v. or a central venous catheter at the discretion of the clinical staff. The study drug is an amino acid (or placebo) and thus, for compatibility purposes, the drug product is treated like parenteral nutrition. Additionally, it is compatible with fluids used for filtration or hemoconcentration during CPB.

No dose adjustments will be allowed; however, study drug may be discontinued as noted above.

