5.1.2.2 Day 0, post-surgery, 0 hours (30 minutes post CPB decannulation)

The following evaluations will be performed 30 minutes post decannulation:

- Blood draw for:
 - plasma L-citrulline (*prior to bolus*); 1.0 mL
- Bolus of L-citrulline at 20 mg/kg or placebo 30 minutes after decannulation from CPB immediately followed by a continuous infusion of L-citrulline at 9 mg/kg/hr or placebo for up to 48 hours. The study drug or placebo infusion will be discontinued once invasive arterial blood pressure monitoring is discontinued or at 48 hours, whichever comes first.
- Hemodynamic monitoring including:
 - Heart rate
 - Systemic BP
 - O₂ saturation
 - CVP measurements
 - PAP measurements (if PA line is placed)

Results will be recorded according to the Institution's standard of care from time of post-op admission to the PICU through 48 hours. Results at 1, 2, 4, 12, 24, and 48 hours *from baseline (in OR)* must be obtained and recorded.

ABGs

PaO₂, PaCO₂, HCO₃, and pH measurements
 ABGs will be drawn according to the Institution's standard of care. All results

obtained from the time of post-op admission to the PICU until removal of the arterial line or through 48 hours (whichever occurs first) will be recorded.

- Thoracotomy output measurements (for the duration of chest tube placement)
- Blood draw for:
 - plasma L-citrulline (5 minutes after bolus); 1.0 mL
- Inotrope and other concomitant medication documentation
- Documentation of ventilator settings. Recorded approximately every hour (+/- 10 minutes) from time of separation from CPB until end of mechanical ventilation or 28 days (whichever occurs first)
- Hypotension assessment (Refractory hypotension is defined as a 20% drop of mean arterial blood pressure [MAP] below specific age-related criteria (Haque and Zaritsky (2007) for greater than 30 minutes) (See below)

– Infants: MAP of 40 Age 1 year: MAP of 40 Age 2 years: MAP of 44 Age 3 years: MAP of 47 Age 4 years: MAP of 50 Age 5 years: MAP of 52 Age 6 years: MAP of 53 Age 7 years: MAP of 52 Age 8 years: MAP of 54 Age 9 years: MAP of 55 Age 10 years: MAP of 56 Age 11 years: MAP of 57 Age 12 years: MAP of 58 Age 13 years: MAP of 59 Age 14 years: MAP of 61 Age 15 years: MAP of 62 Age 16 years: MAP of 63 Age 17-18 years: MAP of 64

Adverse events documentation

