6.2.1.3 Hemodynamic Parameters

Hemodynamic evaluations include heart rate, systemic arterial blood pressure, oxygen saturation, and CVP. If a PA catheter is placed for clinical reasons, PAP will be recorded. Hemodynamic parameters will be assessed prior to anesthesia for CPB and repeatedly until 48 hrs post-operation (Day 2).

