- 3 hrs (14:00-14:59) = 100 (Dobutamine (100) documented 14:01-14:59)
- 4 hrs (15:00-15:59) = 0 (no inotropes documented 15:00-15:59)
- 5 hrs (16:00-16:59) = 100 (Dobutamine documented 16:00-17:00)
- 6 hrs (17:00-17:59) = 100 (Dobutamine documented 16:00-17:00)
- 7 hrs (18:00-18:59) = 0 (no inotropes documented 17:01-18:00)
- ...

The total inotrope score will be imputed to zero after the bypass pump has been removed (separation from CPB). It will also be imputed as zero for patients not using inotropes at all.

The total inotrope score will be summarized at each post-operative hour and analyzed using a Wilcoxon-Rank sum test and an analysis of variance (ANOVA) with a fixed effect for treatment group. Additionally, a repeated measures analysis of variance will be used to compare total inotrope score between placebo and L-citrulline over time.

Hemodynamic improvement

Hemodynamic evaluations include heart rate, systemic arterial blood pressure, oxygen saturation, and central venous pressure. The absolute changes from Baseline at hours 1, 2, 4, 12, 24, and 48 will be compared between groups using an ANOVA with a fixed effect for treatment group and Baseline level.

The last non-missing hemodynamic assessment before start of surgery will be used as Baseline level; i.e. "Date and time of assessment" from section "Hemodynamics" on CRF "Hemodynamics" before "Date of surgery" and "Start time (incision time)" from section "Surgery" on CRF "Surgery". Documented assessments as closest to the target hours 1, 2, 4, 12, 24, and 48 using the following analysis time windows will be used for analysis:

- 1 hrs = 1 min to 89 min (>0 hrs to <1.5 hrs)
- 2 hrs = 90 min to 179 min (≥1.5 hrs to <3.0 hrs)
- 4 hrs = 180 min to 479 min (≥3.0 hrs to <8.0 hrs)
- 12 hrs = 480 min to 1079 min (≥8.0 hrs to <18.0 hrs)
- 24 hrs = 1080 min to 2159 min (≥18.0 hrs to <36.0 hrs)
- 48 hrs = 2160 min to 3599 min (≥36.0 hrs to <60.0 hrs)

An ANOVA per hour adding site and site-by-treatment group interaction will be conducted as a sensitivity analysis. If the p-value for the site-by-treatment group interaction is lower than 0.1 the analysis will also be provided by site. Absolute values and absolute change from Baseline values will be summarized for all observed time points.

Length of time on intubation (invasive ventilation)

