4.8 Missing Values

Efficacy endpoints describing length of time

If a subject did not receive any mechanical ventilation / inotropes / positive pressure ventilation / intubation / vasodilators / chest tube, the corresponding length of time is set to 0. For subjects who died before discharge from the hospital or before Day 28, respectively, the observed length of time will be used for analysis of all time variables.

For time to event analyses censoring information will be used for statistical analyses.

No other imputation of missing values will be used.

Efficacy endpoint inotrope score

The total inotrope score will be set to zero after the bypass pump has been removed. It will also be set to zero for patients not using inotropes at all.

Further secondary efficacy endpoints

No imputation of missing values will be applied for the secondary endpoints hemodynamic improvement, volume of chest tube drainage, and L-citrulline plasma levels.

Safety endpoints

For laboratory data, concentrations below the limit of quantification will be set to zero. Missing safety data or safety assessments will not be estimated nor imputed. All safety summaries and analyses will be based on observed data.

No other imputation of missing values will be used.

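### If central lines come out with recovery, the 24 h and 48 h observed-case ANOVAs of central venous pressure compare groups selected after randomisation, and no analysis addresses this (low priority)

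*SAP*

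**What the plan says.** SAP 4.4.2 defines the endpoint: "Hemodynamic evaluations include heart rate, systemic arterial blood pressure, oxygen saturation, and central venous pressure". For each parameter, "The absolute changes from Baseline at hours 1, 2, 4, 12, 24, and 48 will be compared between groups using an ANOVA" with treatment group and Baseline level as terms. The value used is the one closest to the target hour within a window. The 24 h window runs from 18 h to under 36 h, and the 48 h window from 36 h to under 60 h. The only sensitivity analysis adds site and site-by-treatment. On missing data, SAP 4.8 states: "No imputation of missing values will be applied for the secondary endpoints hemodynamic improvement, volume of chest tube drainage, and L-citrulline plasma levels".

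On collection, Protocol 5.1.2.2 says that results at 1, 2, 4, 12, 24 and 48 hours "must be obtained and recorded", and Protocol 6.2.1.3 says: "Hemodynamic parameters will be assessed prior to anesthesia for CPB and repeatedly until 48 hrs post-operation (Day 2". Footnote 7 of the Schedule of Study Assessments and Procedures lists "CVP, and PAP measurements (if data is available" and has PICU monitoring follow local standard of care.

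On the line itself, Protocol 4.4.1 has a central catheter placed after induction, but the study drug "can run through either a peripheral i.v. or a central venous catheter". No section gives a removal rule, a removal time or an expected share of children with CVP at any hour.

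**The concern.** The protocol recognises dependence on a line for other measurements. Blood gases are recorded until the arterial line is removed, and pulmonary artery pressure is conditional on a PA line. CVP has no such rule, although it cannot be measured once the central line is out.

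The trial's hypothesis is that L-citrulline shortens ventilation and inotrope support and brings children to ICU discharge earlier (Protocol 1.4). If the central line tends to leave when support ends, L-citrulline children with a late CVP would be a smaller and more strongly selected group than placebo children with one. An hour-specific ANOVA on observed values would then compare groups that randomisation no longer balances. If slower recovery goes with a larger rise in CVP, a drug with no effect on CVP would appear to raise it. Twelve or more such p-values could arise from the two late hours, the three efficacy sets and the sensitivity model (2 × 3 × 2 = 12), and nothing would tell the reader how many children lay behind each.

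**Working it through.** **The plan's own figures.** The documents give none for CVP availability. The figure built on Protocol Table 2 is the sample size, and it reproduces. With effect size 0.600, P(X<Y) = Φ(0.6/√2) = 0.6643. Noether's formula gives N = (2.576 + 1.282)² / (3 × 0.1643²) ≈ 183.7, or 92 per group. Nothing below touches it.

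**Step 1. Retention (assumption).** Suppose that the line stays in for the composite duration of Table 2: placebo mean 44.4, SD 63.62; L-citrulline mean 14.3, SD 14.06. For a lognormal, σ² = ln(1 + SD²/mean²) and μ = ln(mean) − σ²/2.
- Placebo: μ = 3.235, σ = 1.056.
- L-citrulline: μ = 2.322, σ = 0.822.

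Share retained at time t = 1 − Φ((ln t − μ)/σ):

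| Time | Placebo | L-citrulline | Children of 95 per arm |
|---|---|---|---|
| 18 h (24 h window opens) | 63% | 25% | 60 vs 23 |
| 24 h | 52% | 15% | 50 vs 14 |
| 36 h (48 h window opens) | 37% | 6% | 35 vs 6 |
| 48 h | 27% | 3% | 26 vs 3 |

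A gamma fit gives 52% vs 29% at 18 h and 37% vs 8% at 36 h. The window openings are the lenient choice, because a reading anywhere in the window counts.

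**Step 2. Bias with no true CVP effect (assumption on correlation).** Let CVP change have SD 1 and correlation ρ with recovery time on the normal scale within each arm. Observed children are the slowest fraction q, whose mean severity is h(q) = φ(z_q)/q, where z_q is the upper q quantile. Bias = ρ × [h(q, L-citrulline) − h(q, placebo)].

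At 18 h, h(0.245) = 1.284 and h(0.628) = 0.602, a difference of 0.681:

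| ρ | Bias (SD) | Rejection at nominal 5% |
|---|---|---|
| 0 | 0 | 5% |
| 0.1 | 0.07 | 6% |
| 0.3 | 0.20 | about 14% |
| 0.5 | 0.34 | about 30% |

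Simulating the same model gives 0.07, 0.21 and 0.33 SD, which agrees to within simulation error. The rejection figures are for a two-group comparison without the Baseline term.

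At 36 h the difference in h is 1.967 − 1.019 = 0.949, so the bias is 0.28 SD at ρ = 0.3 and 0.47 SD at ρ = 0.5, but with only about 6 children against 35.

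**Step 3. How far it depends on the assumptions.** At 18 h the gamma shares give 1.191 − 0.768 = 0.423, so 0.13 SD at ρ = 0.3 and 0.21 SD at ρ = 0.5. With other retention shares, placebo then L-citrulline, and ρ up to 0.5:
- 50% and 30%: at most 0.18 SD, 13% rejection.
- 80% and 70%: at most 0.07 SD, 7%.
- 90% and 85%: at most 0.04 SD, 6%.
- Equal shares: 0 SD, 5%.

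The bias needs both unequal retention and a correlation of CVP with recovery.

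**The case against.** The strongest reply is that the premise is not in the documents. They require results at all six hours with no exception for CVP. The only early line removal they foresee is that of the arterial line, which is a different device. The condition on availability in footnote 7 follows PAP and may not cover CVP. Protocol 4.4.1 also says that doses go by a central catheter or the bypass circuit. A reader might infer that late CVP exists only for children who have not recovered, and that the arms are certain to differ in this. The documents support neither: they do not link the central line to recovery, and with equal retention the bias is zero. This part of the reply stands, and it makes the point conditional. It does not remove it, because a collection requirement cannot produce a CVP after the catheter is out, and no text keeps the catheter in.

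The illustration is also weak evidence on size. Table 2 has 11 children per arm, and that study recorded inotropes only to 48 h. One re-intubated placebo child drives the placebo SD. Without that child (mean 32, SD 26.26) the lognormal placebo share at 48 h falls from 27% to 18%, while the 24 h share is unchanged. Protocol hours run from baseline in the OR, ventilation time runs from separation from bypass, and the SAP windows name no origin. The correlation has no source.

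Finally, the consequence is small. CVP is one of four parameters in one secondary endpoint, SAP 4.4.2 calls all secondary analyses exploratory, and in the scenario shown the bias runs against L-citrulline, so it would not create a false claim of benefit. All of that stands and sets the priority.

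**Conclusion.** The gap is real: CVP is tested hour by hour on observed values, with no imputation and nothing that addresses missingness related to recovery. Whether it biases the result depends on two things that the documents do not settle: whether lines leave with recovery at different rates in the two arms, and whether CVP change is correlated with recovery.

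Under the Table 2 lognormal illustration, the bias in the 24 h window runs from 0 to about a third of an SD, against L-citrulline, for correlations from 0 to 0.5. It is near nil if retention is high or similar in the two arms. These figures show what could happen and do not predict the size. The primary test and its sample size are unaffected and the endpoint is exploratory, so the priority is low. The change is still worth making because it is cheap and the plan otherwise gives no means of seeing the problem.

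**What to change.** In SAP 4.4.2, for CVP only:
- Replace the six separate ANOVAs with one repeated-measures mixed model over all hours, with baseline CVP, treatment, hour, treatment-by-hour and an unstructured covariance. It uses the earlier CVP values of children who have no later one.
- Report the number with a CVP value by arm and hour.
- Label the observed 24 h and 48 h summaries 'in children with a central line' and interpret them descriptively.

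In SAP 4.8, state how CVP missing after central-line removal is treated. The protocol's requirement to obtain all six results should be reconciled with the absence of any provision for children without a line. This is a point about recording and analysis, not about how long a line should stay.

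The cost is one model in place of six tests and one count table; the SAP already plans a repeated-measures analysis for the inotrope score. The limit is that the model assumes missing at random given earlier CVP. In simulation it cut the bias by about 30% to 80% without removing it, and it was never materially worse than the separate ANOVAs. The counts and the descriptive label are therefore needed as well.
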